9.14 Safety Analysis

Safety summaries will be based on the safety set. Safety summaries will include descriptive statistics for values, changes, and incidence of events for all treatment groups combined in addition to summary by treatment group. Conventions for the definition of baseline values and visit windowing are provided in Section 9.1.3. Missing safety data will not be imputed.

9.14.1 Adverse Events

All adverse events will be coded using the latest version of MedDRA. In this dictionary, each verbatim term is coded to a lower level term, and then mapped to a preferred MedDRA term, which is then mapped to an SOC. All adverse events will be included in the data listings but only treatment-emergent adverse events will be included in the summary tables.

A treatment-emergent adverse event (TEAE) is defined as an adverse event with an onset that occurs after receiving study drug (AE start date \geq first dose date) and within 30 days after receiving the last dose of study drug (AE start date – last dose date ≤ 30). A TEAE may also be a pretreatment adverse event or a concurrent medical condition diagnosed prior to the date of first dose of study drug that increases in severity after the start of dosing. Adverse events data with onset occurring more than 30 days after last dose of study drug (AE start date – last dose date > 30) will be listed, but not included in the summary tables. Adverse events with missing onset dates will be summarized regardless of severity and relationship to study medication.

Serious adverse events (SAEs) with onset that occurs after receiving study drug (AE start date \geq first dose date) and within 30 days after receiving the last dose of study drug (AE start date - last dose date ≤ 30) will be summarized.

At the adverse event level, the summary tables will present the number of subjects reporting each of these MedDRA events, ie, the number of subjects reporting one or more events which map to the given MedDRA term.

At the SOC level, the summary tables will present the number of subjects reporting one or more events that map to the given SOC. That is, the number of subjects reported at the SOC level will be less than or equal to the sum of the subject counts across all adverse events within that SOC.

In selected summaries (TEAEs overview, and TEAEs by SOC and preferred term), adverse events will be summarized by the number of events reported in addition to the number and percentage of subjects with events.

For the summary of TEAEs by SOC, preferred term and maximum intensity, if a subject experiences more than one episode of a particular coded adverse event, the subject will be counted only once by the maximum intensity of the episode (preferred term). Similarly, if a subject has more than one adverse event within an SOC, the subject will be counted only once by the maximum intensity in that SOC. Adverse events with missing severity will be classified as having the highest severity.

TEAEs classified in the eCRF as related to the study medication will also be summarized by preferred term and SOC. If a subject experiences more than one episode of a particular coded adverse event, the subject will be counted only once by the most related report for the preferred term. Similarly, if a subject has more than one adverse event within an SOC, the subject will be counted only once by the most related report in that SOC. Adverse events with missing relationship will be classified as being related to study drug.

The following summaries will be presented:

- Overview of TEAEs during the study - number and percentage of subjects, number of events.
- TEAEs by SOC and preferred term - number and percentage of subjects, number of events.
- TEAEs by SOC and preferred term by gender (male and female) - number and percentage of subjects, number of events.
- TEAEs by SOC and preferred term by age group (<75, ≥75) - number and percentage of subjects, number of events.
- TEAEs by SOC - number and percentage of subjects.
- TEAEs by preferred term - number and percentage of subjects.
- Intensity of TEAEs by SOC and preferred term - number and percentage of subjects.
- Drug-related TEAEs by SOC and preferred term - number and percentage of subjects, number of events.
- TEAEs leading to study discontinuation by SOC and preferred term - number and percentage of subjects, number of events.
- Treatment-emergent SAEs by SOC and preferred term - number and percentage of subjects, number of events.

- Most frequent TEAEs and non-serious TEAEs ($\geq 5\%$ based on total number of safety set subjects in any treatment group) by SOC and preferred term - number and percentage of subjects, number of events.
- Adverse Events of Special Interest using the following categories defined in the protocol:
 - Congestive Heart Failure.
 - Macular Edema.
 - Hepatic Effects.
 - Bone Fractures.
 - Bladder Cancer.
 - Hypoglycemic Events.

SOCs will be sorted by alphabetical order. Within an SOC, adverse events will be sorted in descending order of total number of subjects with preferred term among all the treatment groups.

Subjects mappings will be provided for TEAEs, TEAEs leading to study drug discontinuation, and serious TEAEs.

All adverse events will be listed by treatment, study center, subject number and onset date of the adverse event. The listing will contain: subject identifier, age, gender, body weight, race, adverse event (preferred term and reported term), SOC, onset date, end date or whether the event was ongoing, duration, type (pretreatment event, adverse event) frequency (intermittent, continuous), intensity (mild, moderate or severe), related to study procedure (yes/no; if yes, specify), relationship to study drug (not related, related), action taken concerning study drug (drug withdrawn, dose not changed, unknown, not applicable, or dose interrupted), the outcome (recovered/resolved, recovering/resolving, not recovered/not resolved, recovered with sequelae, fatal, or unknown), increased liver function tests (yes, no), whether the adverse event was an SAE, and whether the event was an adverse event of special interest (AESI).

Listings for TEAEs leading to study discontinuation, SAEs, deaths, and AEs of special interest will also be presented. A description of the AESIs for this study are provided in Section 10.2.1.3 of the protocol and consist of the following categories: congestive heart failure, macular edema, hepatic effects, bone fractures, bladder cancer, and hypoglycemia.

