7.5 Procedures for Discontinuation or Withdrawal of a Subject

The investigator may terminate a subject's study participation at any time during the study when the subject meets the study termination criteria described in Section 7.4. In addition, a subject may discontinue his or her participation without giving a reason at any time during the study. Should a subject's participation be discontinued, the primary criterion for termination must be recorded. In addition, efforts should be made to perform all procedures scheduled for the EW Visit. Discontinued or withdrawn subjects will not be replaced.

Subjects who discontinue study medication prematurely should be contacted by the study site every 6 months until the conclusion of the study via telephone to assess the general well-being of the subject as well as to obtain any changes in medications related to cognitive health. In the event the subject is not able to be reached, the subject's caregiver or primary care physician can be contacted to obtain this information.

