In general, the baseline value for a variable is defined as the last observation prior to the first dose of double-blind study medication (visit date \leq first dose date), including the screening value, if necessary.

Adverse events that start more than 30 days after the last dose of double-blind study medication (start date – last dose date >30) will be listed, but excluded from the summaries and analyses. For efficacy and other safety data, data that are obtained more than 7 days after the last dose of double-blind study medication (visit date – last dose date > 7) will be listed, but excluded from summaries and analyses. (Note: This efficacy data window only applies to determining which data are included/excluded from the summary statistics and formal statistical analysis tables for a given efficacy endpoint. All events of MCI due to AD (or AD dementia) as determined by the adjudication committee will be included in the time-to-event analyses, without regard to the date of last dose of double-blind study medication.)

If the date of first dose of double-blind study drug collected in the eCRF is missing, then for summary purposes the day after the first dispense date will be used as an estimate for the date of first dose. However, if all dispensed study drug is returned, then the subject is assumed to have not taken any study drug, and the first dose date will not be imputed.

If the date of last double-blind study drug dose collected in the eCRF is missing, then the earliest of the following dates will be used for the last dose date for analysis and summary purposes: date of death, date of last visit (recorded in the eCRF), last double-blind study drug return date, and the last double-blind study drug dispense date (following the last drug return date) + 200 days (ie, the double-blind study drug dispensing interval corresponding to the number of study drug tablets dispensed).

The study window convention will not be applied to the eCRF data listings. The data listings for eCRF data will display the raw data as collected and entered in the eCRF. For efficacy listings, windowed visits will also be shown on the listings.

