9.4 Disposition of Subjects

A subject disposition summary presented by treatment group and overall will be provided. The categories will include all subjects who were randomized, subjects who were not treated, subjects who discontinued from the study categorized by reason, and subjects who completed the study. Post-randomization discontinuation reasons include pretreatment event or adverse event, major protocol deviations, lost to follow-up, lack of efficacy, voluntary withdrawal, study termination, pregnancy, and other. A listing will be presented to describe study treatment, date of first dose, date of last dose, date of completion or early withdrawal, and the reason for early discontinuation for each subject.

A summary of screening failures and listings of inclusion/exclusion criteria responses for subjects with violations will also be provided.

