A subject who does not have an event of MCI due to AD (including AD itself) will be censored for that event at the date of last visit at which a case of MCI due to AD could have been assessed (i.e., the last regularly scheduled visit at which the cognitive battery was assessed or the last unscheduled comprehensive medical follow-up visit at which the CDR was assessed, whichever is later). For subjects who discontinue from the study prior to their first assessment of the cognitive battery or CDR, the date of last contact will be used as the censoring time. At the time of the futility analysis, a subject who has not discontinued from the study and has not had an event of MCI due to AD (or AD) will be censored for that event at the date of the last visit at which a case of MCI due to AD could have been assessed prior to the futility analysis clinical database cut date (ie, the last regularly scheduled visit at which the cognitive battery was assessed or the last unscheduled comprehensive medical follow-up visit at which the CDR was assessed prior to the futility analysis clinical database cut date, whichever is later).

For subjects who die during the trial, the date of death is considered a censoring time for the event of MCI due to AD (rather than as a component of the event of MCI due to AD itself).

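### Deaths are only listed and events starting more than 30 days after last dose are left out of the summaries, so no mortality summary by randomised arm is planned

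*SAP*

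**What the plan says.** SAP 9.14.1 gives a list of adverse event summary tables, and no item in it is a table of deaths. Deaths come in only afterwards: "Listings for TEAEs leading to study discontinuation, SAEs, deaths, and AEs of special interest will also be presented". The nearest table that can contain a death is "Treatment-emergent SAEs by SOC and preferred term - number and percentage of subjects, number of events", which is not split by outcome.

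The 30-day rule appears twice. Under SAP 9.14.1, events starting more than 30 days after last dose "will be listed, but not included in the summary tables"; under SAP 9.1.3 they "will be listed, but excluded from the summaries and analyses". Protocol 13.1.6 uses the same window to define treatment-emergent events.

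Three other SAP sections bear on the point:
- 9.4 gives the reasons for discontinuation. After adverse events and major protocol deviations they run "lost to follow-up, lack of efficacy, voluntary withdrawal, study termination, pregnancy, and other". Death is not among them.
- 9.3 analyses safety by treatment received, not by randomised arm.
- 9.9.4 handles death in the primary analysis: "For subjects who die during the trial, the date of death is considered a censoring time for the event of MCI due to AD".

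On follow-up, Protocol 7.5 says: "Subjects who discontinue study medication prematurely should be contacted by the study site every 6 months until the conclusion of the study via telephone". The call covers general well-being and medication changes bearing on cognition; a caregiver or the primary care physician may be asked instead. Subjects with an adjudicated endpoint leave as completers after an end-of-study visit (Protocol 6.2.4). They get one safety call two weeks later, which is omitted if they enter the extension (Protocol 9.3.7). Routine adverse event collection also ends two weeks after a subject finishes or withdraws (Protocol 10.2.1.1). After that, a serious event reaches the sponsor only if it is reported spontaneously and judged related to participation (Protocol 10.2.2).

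**The concern.** Protocol 4.2.2 sets an unusually high safety bar because the subjects are cognitively normal, and Protocol 4.1 names heart failure and bladder cancer among the known warnings for the drug. Protocol 10.2.1.3 withdraws subjects with new or worsening heart failure, with macular edema, or with bladder cancer that cannot be excluded. Tables confined to drug exposure plus 30 days are therefore cut short by the harms of most interest, possibly to a different extent in the two arms. All-cause mortality by randomised arm is not cut short in that way, provided that vital status is followed.

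Mortality also helps in reading the primary result. Subjects enter at 65 to 83 years and death censors MCI due to AD, so a reader of the hazard ratio will want to see whether deaths differed between arms. Followed exactly, the plan gives that reader individual listings to count by hand.

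**Working it through.** **Is there a by-arm death summary anywhere?** Set side by side, the sections give: a listing of deaths (SAP 9.14.1); event tables that count on-treatment fatal events under their preferred term without marking them fatal (SAP 9.14.1); no death category in disposition (SAP 9.4); and death as a censoring time (SAP 9.9.4). Neither document specifies a count, rate, curve or test of deaths by arm.

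**The plan's drop-out figure.** Protocol 13.3 and SAP 8.0 give 12% a year and 47% over 5 years. Check: 1 − 0.88^5 = 47.2%. It reproduces.

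**Person-time outside the window.** Assume exponential drop-out, that drop-out means stopping drug, and a 5-year horizon.
- Rate d = −ln(0.88) = 0.1278 per year.
- Mean time on drug = (1 − exp(−5d))/d = 0.4723/0.1278 = 3.69 years, so 1 − 3.69/5 = 26% of follow-up comes after last dose.
- The 30-day tail is w = 30/365.25 = 0.082 years. It adds w × [1 − exp(−d(5 − w))] = 0.082 × 0.467 = 0.038 years.
- Share outside the window = 1 − (3.694 + 0.038)/5 = 25%.

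**Deaths.** The documents give no mortality rate, so a range m of 1% to 3% a year is assumed, equal in both arms, with 1,470 high-risk subjects per arm (Protocol 6.1).
- All followed: 1,470 × [1 − exp(−5m)].
- Inside the window: 1,470 × { m/(m+d) × [1 − exp(−5(m+d))] + d/(m+d) × [1 − exp(−(m+d)(5 − w))] × [1 − exp(−mw)] }.
- 95% CI factor for a mortality hazard ratio: exp(1.96 × √(2/deaths per arm)).

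| Assumed mortality per year | Deaths per arm, all followed | Inside window | Outside window | CI factor, all followed | CI factor, window only |
|---|---|---|---|---|---|
| 1% | 71.7 | 53.7 | 18.0 | 1.39 | 1.46 |
| 2% | 139.9 | 105.0 | 34.9 | 1.26 | 1.31 |
| 3% | 204.8 | 154.1 | 50.7 | 1.21 | 1.25 |

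About a quarter of deaths fall outside the window at each rate. The calculation places each death at the onset of its fatal event and ignores subjects who leave at the endpoint.

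**Is vital status already secured?** Three groups differ. Subjects still in the study are seen every 6 months. Premature drug stoppers are telephoned every 6 months, but neither vital status nor date of death is a named item. Endpoint completers, about 202 high-risk subjects at the event target, have no specified contact in this trial beyond the two-week call. The all-followed column is therefore a ceiling, not what the present follow-up would deliver.

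**The case against.** The best defence is that the plan matches its own objective. Protocol 5.1.3.1 frames safety as during treatment, and a 30-day window fits that. Fatal on-treatment events are not lost: they enter the treatment-emergent tables by preferred term, gender, age group and intensity, the serious event table and, where they qualify, the drug-related, discontinuation and special-interest tables. A death after day 30 from an event that began inside the window is still counted. The contents of the treatment-emergent overview table are not given, so a deaths row there cannot be ruled out. The DSMB reviews all safety data (Protocol 11.2), and its charter is not among the documents. All of this stands, and none of it supplies a specified summary of deaths by randomised arm.

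A second argument limits the primary-endpoint concern. Under SAP 9.9.4, subjects without an event are censored at the last visit at which a case could have been assessed, so deaths long after withdrawal have little bearing on that result. This stands too; the deaths that matter there are those that occur on study.

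A reader might infer from the 6-monthly calls that every subject's status is already sought to study end, so that only a table is missing. The documents do not support this. The calls are for premature drug stoppers, they do not name vital status, and endpoint completers are outside them. With adverse event collection closing two weeks after withdrawal, some late deaths may not reach even the listing.

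**Conclusion.** The point holds as a reporting gap with a data-capture gap behind it. The plan specifies no mortality summary or comparison by randomised treatment, does not identify on-treatment fatal events as fatal in its tables, and does not tabulate events starting more than 30 days after last dose.

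The size, about 25% of 5-year person-time and about 18 to 51 of 72 to 205 deaths per arm, rests on four assumptions: drop-out means stopping drug, mortality is 1% to 3% a year and equal in both arms, each arm has 1,470 subjects, and vital status is complete. None of these mortality rates comes from the documents, and the last assumption is not met by the present follow-up. The loss of precision from the window alone is modest (CI factor 1.26 against 1.31 at 2% a year). The larger loss is that no by-arm comparison is specified at all.

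Two further inferences go too far. It cannot be said that fatal events are counted only in the serious event table, since they enter several others. Nor can it be said that mortality is never compared, since what the DSMB sees is unknown. The change is worth making because it is cheap and strengthens the safety conclusion; it does not affect the validity of the primary test.

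**What to change.** Add to SAP 9.14 an analysis of all known deaths from randomisation, by randomised arm in the high-risk stratum, whatever the time since last dose. Report the number of deaths, the rate per 100 person-years, a Kaplan-Meier curve and a Cox hazard ratio with 95% CI, censoring at the last date known alive. Show by arm how complete vital status is.

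In Protocol 7.5, name vital status and date of death as items in the existing 6-monthly contact. Unless that contact is extended to endpoint completers, label the analysis as based on known deaths and censor completers at last contact.

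The cost is one table, one figure and a field on the call form, with incomplete follow-up stated as a limitation. Part of the input is already planned: SAP 9.1.3 and 9.9.4 use the date of death, and the adverse event listing in SAP 9.14.1 records fatal outcomes. Extending contact to completers would be a further, modest protocol change; a SAP edit alone cannot make the mortality follow-up complete.

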9.14.2 Clinical Laboratory Evaluations

The following clinical laboratory parameters will be summarized:

- Serum chemistry including alanine aminotransferase (ALT), alkaline phosphatase, aspartate aminotransferase (AST), total bilirubin, GGT, total protein, albumin, creatinine, blood urea nitrogen (BUN), potassium, sodium, glucose, calcium, vitamin B12, folate, parathyroid hormone (PTH), thyroid stimulating hormone (TSH), and free thyroxine (free T4). (Direct bilirubin will be assessed only if total bilirubin ≥ 2.0 mg/dL. Vitamin B12, folate, and RPR is

collected only at Baseline and as part of the comprehensive medical follow-up evaluation to rule out other causes of dementia).

- Hematology including red blood cells, white blood cells, neutrophils, eosinophils, basophils, lymphocytes, monocytes, hemoglobin, hematocrit, platelets, and HbA1c. (HbA1c is collected only at Baseline.)
- Urinalysis including pH, specific gravity, glucose, and nitrite. (Protein and blood values will not be summarized but will be included in the listings.)

For each laboratory parameter, the following will be displayed for each scheduled time point (each visit and end of study).

- Summary statistics (n, mean, SD, median, minimum, and maximum) by treatment group and overall for the actual values and change-from-Baseline values.
- Shift tables for the change from Baseline to each post-baseline time point will be presented. For these tables each subject will be categorized as low, normal, or high for the baseline value and low, normal, or high for each post-Baseline time point, according to the central laboratory reference ranges. The number of subjects in each of the combinations of shifts will be presented.
- Markedly abnormal values for laboratory parameters, as defined in [Appendix A](#), will be summarized by treatment group and overall. The number and percentage of subjects with MAV values observed post-Baseline in each of the applicable laboratory parameters will be presented.
- Number and percentage of subjects with elevated liver enzyme lab values will be presented using the criteria described in the protocol.

Subject mappings will be provided for markedly abnormal lab values and elevated liver enzyme lab values.

A listing of all laboratory data will be provided. Laboratory data outside of the normal reference range will be flagged on the listing along with values meeting MAV criteria. The listing will also include the age (at consent) and gender of the subject. Listings of MAV laboratory values will also be presented. Direct bilirubin and rapid plasma regain (RPR) will not be summarized but will be listed.

The following listings of information from the liver function test eCRF pages will be presented: Study drug interruption, signs and symptoms, event history, test results and reports, and additional comments.

When lab values are recorded in the form of “<x” or “>y”, “x” will be used for “<x” and “y” will be used for “>y” in the MAV summary tables. However, these values will be displayed as is when the individual subject data listings are presented.

Summaries and listings of laboratory data will be presented, as appropriate, in Systeme International (SI) and conventional units.

